9.2. Setting

The assessment surveys will be executed as soon as 12 months but no later than 18 months from launch of the product in Germany, the UK (if product uptake does not allow for participation, another comparable EU country will be selected), and a third EU country to be determined. Countries will be selected based on a sufficient number of prescribers and volume of prescriptions to allow for a successful enrolment of HCPs and patients. Pan-European diabetes treatment guidelines issued by professional organizations such as European Association for the Study of Diabetes (EASD; Inzucchi et al. 2015) and the European Society of Cardiology for the management of patients with diabetes, such that the difference in clinical practices in different EU countries should be negligible (ESC Task Force 2013). Therefore, selection bias will be largely prevented due to common clinical practice, standardized messaging, and survey implementation. The timing of the initiation of the survey depends on the product launch dates and the product uptake in each country.

The target population in each selected county will receive the same risk communication, to be provided in their official national language. Additionally, the same survey will be used in all 3 countries in order to test the target population on the same key safety messages. As such, variability of survey results based on geography is not anticipated and therefore 3 countries will be representative of the EU.

The UBC will administer the surveys to the study populations who respond to the invitations to participate in the study. Every effort will be made to ensure the samples participating from each country in the survey will be proportional to the expected eligible population among participating countries. The EDC system will be programmed to ensure desired distribution by requiring a minimum number of eligible participants from each country.

HCPs:

Surveys targeting eligible HCPs will be administered via the Internet, which will allow respondents to participate at a time and location that is convenient for them, and by telephone, to allow participation of respondents who do not have Internet access. Both modalities will offer the same survey.

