9.7. Data analysis

Data collected from the survey will be reported as descriptive statistics. Frequency distributions with 95% CIs will be calculated for respondent responses to all questions that address the survey objectives. Responses to each question relating to the key risk messages will be categorised as “Correct response” and “Incorrect response”. “I don’t know” is generally categorised as an incorrect response unless otherwise specified.

In addition to the overall analysis, survey data will be analysed to determine if there are any differences by country and, for HCPs, medical speciality. Sub-group analyses will include all requested subgroups including patients switched from other 100 units/ml insulins, Humalog 100 U/ml, how long patients were on insulin, and which other insulins have been used as captured in the questionnaire. Additionally, a subgroup analysis will be performed to identify possible differences in the responses based on length of Humalog 200 units/ml use.

The following will be reported as part of the analysis:

HCPs:

- *Survey administration*
 - The number of survey invitations issued by strata (i.e., by country and specialty)
 - The number of survey invitations returned due to incorrect mailing address of HCPs invited to participate in the survey
 - The number of HCPs who responded to the invitation to participate in the survey
 - The number of HCPs eligible for participation in the survey
 - The number of ineligible HCPs along with the reasons for ineligibility
 - The number of eligible HCPs who completed the survey
- *Demographic characteristics of participants*
 - Distribution of participants by age groups
 - Distribution of participants by sex
 - Distribution of participants by practice setting
 - Distribution of participants by country
 - Distribution of participants by medical specialty
 - Distribution of participants by years in medical practice
 - Distribution of participants by number of patients treated with Humalog 200 units/ml KwikPen
- *Responses to questions pertaining to the survey objectives:*
 - Awareness of the DHPC on the correct use of Humalog (insulin lispro) 200 units/ml KwikPen
 - Understanding of the risk messages
 - Self-reported practices with respect to communication of the key risk messages in clinical practice

Patients:

- *Survey administration*
 - The number of HCPs asked to invite patients to participate
 - The number of invitations provided to HCPs

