Thank you in advance for your participation. Please note the application will time out after 30 minutes of inactivity.

If you are ready to begin the survey at this time, please click continue. If not, click Return Later.

Please note: Do not use the browser's back button during this survey.

[END WELCOME PAGE]

16. Are you familiar with the patient communication: *IMPORTANT SAFETY INFORMATION FOR Humalog 200 units/ml KwikPen (insulin lispro)* provided by Eli Lilly and Company?

- Yes
- No **[GO TO Q18]**
- I don't know **[GO TO Q18]**

17. Did you read the patient communication: *IMPORTANT SAFETY INFORMATION FOR Humalog 200 units/ml KwikPen (insulin lispro)* provided by Eli Lilly and Company?

- Yes
- No
- I don't know

18. **[DISPLAY ONLY IN [ENTER COUNTRY THAT HAS WEBSITE]** Are you aware of the website [ENTER WEBSITE], at which patients can access the patient communication: *IMPORTANT SAFETY INFORMATION FOR Humalog 200 units/ml KwikPen (insulin lispro)*?

- Yes
- No
- I don't know

[DO NOT DISPLAY IF 0 IS SELECTED IN Q8]

[DISPLAY ONLY IN [ENTER COUNTRY THAT DOES NOT HAVE WEBSITE]
Do you or another healthcare professional at your practice provide the patient communication: *IMPORTANT SAFETY INFORMATION FOR Humalog 200 units/ml KwikPen (insulin lispro)*, to patients receiving their first prescription of Humalog 200 units/ml KwikPen?

19.

Do you or someone at your practice provide the patient communication: *IMPORTANT SAFETY INFORMATION FOR Humalog 200 units/ml KwikPen (insulin lispro)* or the website at which the communication can be accessed, to patients receiving their first prescription?

- Yes

- No
- I don't know

[DO NOT DISPLAY IF 0 IS SELECTED IN Q8]

20. Do you or another healthcare professional at your practice discuss the patient communication: *IMPORTANT SAFETY INFORMATION FOR Humalog 200 units/ml KwikPen (insulin lispro)* with patients at the time of initial prescription of Humalog 200 units/ml KwikPen?

- Yes
- No
- I don't know

[PHONE ONLY: BEGIN SAFETY EVENT]

(INTERVIEWER: Please record if respondent spontaneously reported a safety event or product complaint during the course of this interview.)

- Yes
- No **[GO TO END SAFETY EVENT SECTION]**

Enter Safety Event or Product Complaint Verbatim

[MULTILINE INPUT]

(INTERVIEWER: Refer to Project Specific Procedure for next steps.)

[END SAFETY EVENT]

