- Some secondary school (or EU equivalent) or less
 - Finished secondary school
 - Some university or completed technical/trade school
 - Graduated university
 - Post graduate studies
 - Prefer not to answer
11. In what country do you live?
- [DROP-DOWN LIST INPUT WITH COUNTRIES TABLE]**
12. Which of the following groups best describes your age?

- Under 18 **[TERMINATE AFTER Q12]**
 - 18 – 29
 - 30 – 39
 - 40 – 49
 - 50 – 59
 - 60 – 69
 - 70 or older
 - Prefer not to answer **[TERMINATE AFTER Q12]**
13. Have you or any of your immediate family members ever worked for Eli Lilly and Company (Lilly), United BioSource Corporation (UBC), or the European Medicines Agency (EMA)?
- Yes **[TERMINATE]**
 - No
 - I don't know **[TERMINATE]**

[END SCREENING QUESTIONS]

[BEGIN SURVEY CONTENT]

[PREAMBLE 2]

The following questions are about Humalog 200 units/ml KwikPen.

14. Please answer True, False, or I don't know for each of the following statements about Humalog 200 units/ml KwikPen.

	[RANDOMISE LIST]	True	False	I don't know
A	Humalog 200 units/ml should only be injected using the			

prefilled KwikPen device in which it is supplied.

- B Your dose of insulin does not need to be converted when changing from one strength of Humalog to the other (for example, changing from Humalog 100 U/ml to Humalog 200 units/ml KwikPen).

15. Please answer Yes, No, or I don't know for each of the following statements about the patient communication titled *IMPORTANT SAFETY INFORMATION FOR Humalog 200 units/ml KwikPen (insulin lispro)*.

- | | Yes | No | I don't know |
|---|-----------------------|-----------------------|-----------------------|
| 
[RANDOMISE LIST]
 
[DISPLAY ONLY IN [ENTER COUNTRIES THAT DO NOT HAVE WEBSITE]]The first time I was prescribed Humalog 200 units/ml KwikPen, my doctor or nurse provided me with a paper copy of IMPORTANT SAFETY INFORMATION FOR Humalog 200 units/ml KwikPen (insulin lispro).
 |  |  |  |
| 
A [DISPLAY ONLY IN [ENTER COUNTRIES THAT HAVE WEBSITE]]The first time I was prescribed Humalog 200 units/ml KwikPen, my doctor or nurse provided me with a paper copy or told me to access the website to view IMPORTANT SAFETY INFORMATION FOR Humalog 200 units/ml KwikPen (insulin lispro).
 |  |  |  |

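### The two country versions of HCP survey Q19 differ in who provides the communication and in whether the product is named, beyond the intended website phrase

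*Protocol*

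**What the plan says.** Protocol Sections 4.5 and 9.1 list, among the HCP endpoints, the report that patients were given the communication, or a means of reaching it, at their first prescription of this product. Q19 in Appendix I.1 is the item that measures this.

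- **Version for countries without a website**, marked "DISPLAY ONLY IN [ENTER COUNTRY THAT DOES NOT HAVE WEBSITE". It asks "Do you or another healthcare professional at your practice provide the patient communication" and continues "to patients receiving their first prescription of Humalog 200 units/ml KwikPen".
- **Version for countries with a website.** It asks "Do you or someone at your practice provide the patient communication" and continues "or the website at which the communication can be accessed, to patients receiving their first prescription".

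Section 9.7 says that "survey data will be analysed to determine if there are any differences by country". Section 9.6 says that results are both stratified by country and combined.

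**The concern.** When a country-dependent item measures an endpoint, its versions should differ only where local circumstances require it. Here the local circumstance is the website, and the channel phrase deals with that. Two further elements change without explanation: the other person who may provide the document (a healthcare professional in one version, anyone at the practice in the other), and the product attached to the first prescription.

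Website availability is a property of the country, so each country sees one version only. If the three countries are not all alike in this respect, a difference in reported provision between them could be a difference in practice, in wording, or both, and no analysis of the collected data could separate them. The pooled percentage would average answers to two slightly different questions.

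**Working it through.** **1. The two Q19 versions against the endpoint and the neighbouring items**

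| Element | Q19, no website | Q19, website | Endpoint (9.1) | HCP Q20 | Patient Q15A, both versions |
|---|---|---|---|---|---|
| Provider | respondent or another HCP | respondent or anyone at the practice | HCP | respondent or another HCP | doctor or nurse |
| Product at first prescription | named | not named | named | named | named |
| Channel | communication | communication or website | communication or means of access | not applicable | paper, or paper or website |

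The channel row varies as the endpoint intends. In the provider and product rows, the website version of Q19 is the only one that departs from the rest. Q15A has the same kind of country split and shows that the website phrase can be added without touching provider or product.

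**2. Direction.** If respondents read the items literally, anyone who could say Yes to the narrower provider and product wording could also say Yes to the broader one. The provider and product changes can therefore raise the Yes percentage in website countries or leave it unchanged. They should not lower it.

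**3. The plan's own precision.** Equation 1 in Section 9.5 at n = 280 and 50%: 1.96 × √(0.5 × 0.5 / 280) = 5.86 points. Table 1 gives 5.9%, so the figure reproduces. The other rows recompute to 5.74, 5.37, 4.69 and 3.51 points and match the table. Fewer than 280 will answer Q19 if some respondents select 0 at Q8, because they are not shown it.

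**4. Possible size, by assumption only.** The documents give no wording effect. Let *d* be the extra Yes percentage under the broader wording and *w* the share of respondents who see it. The pooled shift is *w* × *d*:

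| Share *w* | *d* = 5 | *d* = 10 | *d* = 15 |
|---|---|---|---|
| 1/3 | 1.7 | 3.3 | 5.0 |
| 1/2 | 2.5 | 5.0 | 7.5 |
| 2/3 | 3.3 | 6.7 | 10.0 |

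The whole of *d* would appear in a contrast between website and no-website countries. If the 280 were split equally by country (also an assumption; the plan intends a proportional split), one country against two would be about 93 against 187. At 50% the half-width of that difference is 1.96 × √[0.25 × (1/93 + 1/187)] = 12.4 points. A single country of 93 has a half-width of 1.96 × √(0.25 / 93) = 10.2 points. So most of the assumed range for *d* lies within the sampling uncertainty of a country contrast.

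**The case against.** The case for leaving the item alone is substantial, and much of it stands.

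- **Channel.** A reader might count the website phrase as a defect. It is not: the endpoint accepts a means of access, and Section 7 provides a web link only where approved. For the same reason patient Q15A, whose versions differ in channel alone, is not affected. Asking about paper and website in separate items would be a preference, because the research question in Section 8 does not ask which channel worked.
- **Same survey.** A reader might infer a contradiction with Section 9.2, which says "the same survey will be used in all 3 countries in order to test the target population on the same key safety messages". That sentence is tied to the key safety messages, and the provision item does not test them. The statement can stand.
- **Display rule.** The website version shows no display instruction in the text as read. The layout around Q19 is broken there, and the companion version makes the intended audience clear. Nothing should be built on this.
- **Product name.** The title of the communication contains the product name, so few respondents are likely to think of another product's first prescription. This softens the product difference but leaves the provider difference.
- **Contingency.** The UK may be replaced, the third country is undecided and the website countries are placeholders. If all three have a website, or none does, only one version is used and there is no confounding. The website version would still be looser than the endpoint if it were the one used.
- **Analysis.** The study is descriptive, and tables by country already separate the versions. That is true, but it shows the versions apart without showing whether a difference comes from wording or practice.

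**Conclusion.** The point holds in a narrow form. One HCP item that measures a listed endpoint has two versions that differ in provider and in naming the product, with no stated reason, and the website version is looser than the endpoint, Q20 and Q15A. If the selected countries differ in website availability, a country difference in provision, or the pooled percentage, may partly reflect wording. The likely direction is upward in website countries, assuming literal reading. The size is unknown, and the figures above are illustrations.

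A reader might go further and conclude that wording alone would carry a country across the majority line, for example from 50% to 60%. The documents do not support that: they give no such effect and no country-level majority criterion, and the 5.9-point half-width in Table 1 applies to all 280 respondents, not to one country.

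The knowledge items and the sample size are not affected. Severity is minor.

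**What to change.** In both versions of Q19 use the provider wording "Do you or another healthcare professional at your practice provide the patient communication" and the prescription wording "to patients receiving their first prescription of Humalog 200 units/ml KwikPen". Let the website version differ only by adding the phrase that offers the website as an alternative to the communication. Report provision by item version as well as pooled, so that a reader can see which countries answered which version.

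The appendix is still a draft survey, so the cost is a text edit before programming and translation and one extra breakdown in the tables. It needs no extra items or respondents. It should be done before fielding, because respondents cannot return to an answered question (Section 9.4.1) and will not be queried (Section 9.6).

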APPENDIX I.3 PATIENT SURVEY

SURVEY LEGEND

- **[PROGRAMMER]** is used to indicate directions to the programmer and is set in bold, red, uppercase letters between square brackets.
- **(INTERVIEWER)** is used to indicate directions to the phone interviewer and is set in bold, blue, text between parentheses. This text appears when content is to be administered by phone only (for example, spontaneous safety event reporting).
- **[ONLINE]** indicates a question/section is worded specifically for administering the survey online.
- **[TELEPHONE]** indicates a question/section is worded specifically for administering the survey over the telephone.
- **[BEGIN SURVEY CONTENT]** and **[END SURVEY CONTENT]** are used to indicate to the programmer the type of survey administration and the beginning and end of the survey or sections within the survey content.
- **[TERMINATE]** is displayed next to responses that should cause the survey to end. The following termination language will be programmed into the survey or read by the interviewer.

Thank you very much for your time today. Based on your answer, you are not eligible to take this survey. We appreciate your interest in the survey.

- **[RANDOMISE LIST]** is inserted before questions to indicate to the programmer that the responses should be randomised. Responses such as “I don’t know,” “Prefer not to answer” or “None of the above” will always appear at the end of the randomised responses.
- **[GO TO Qx]** (skip logic) is inserted after a response to indicate to the programmer that the survey should skip to the indicated question (for example, **[GO TO Q17]** skips to question 17). If no skip logic is indicated the survey continues to the next question in the sequence.

SURVEY LEGEND

- **[MULTILINE INPUT]** indicates to the programmer that multiple lines should be provided for data entry.
- **[FREE TEXT]** indicates to the programmer that one line should be provided for data entry.
- **[DROP-DOWN LIST INPUT WITH COUNTRIES TABLE]** indicates to the programmer that the response should be a drop-down list containing the countries in the table below.

United Kingdom
(or other comparable EU
country based on product
uptake)

Germany

TBD

The following is used to categorise survey populations into standard geographic regions but it is not displayed in the survey.

[WELCOME PAGE]

This survey should take approximately 15 minutes to complete. If you cannot complete the survey at this time, please return when you can. Once you begin the survey you will need to answer all questions; you will not be able to access the survey again if you exit.

Thank you in advance for your participation. Please note the application will time out after 30 minutes of inactivity.

If you are ready to begin the survey at this time, please click continue. If not, click Return Later.

Please note: Do not use the browser's back button during this survey.

[END WELCOME PAGE]

[BEGIN SCREENING QUESTIONS]

Please provide a response to all questions and statements.

1. Do you agree to take part in this survey about Humalog[®] 200 units/ml KwikPen[™]?
 - Yes
 - No **[TERMINATE]**

2. Have you been diagnosed with diabetes?
 - Yes
 - No **[GO TO Q9; TERMINATE AFTER Q12]**
 - I don't know **[GO TO Q9; TERMINATE AFTER Q12]**

3. How long have you had diabetes?
 - Less than 1 year
 - 1 – 5 years
 - 6 – 10 years
 - 11 – 15 years
 - More than 15 years
 - I don't know
 - I don't have diabetes**[GO TO Q9; TERMINATE AFTER Q12]**

4. Do you use injectable insulin to treat your diabetes?
 - Yes
 - No **[GO TO Q6; TERMINATE AFTER Q12]**
 - I don't know **[TERMINATE AFTER Q12]**
 - I don't have diabetes **[TERMINATE AFTER Q12]**

5. For how long have you been using injectable insulin to manage your diabetes?
- Less than 1 year
 - 1 – 5 years
 - 6 – 10 years
 - 11 – 15 years
 - More than 15 years
 - I don't know
 - I don't have diabetes/I don't use insulin **[GO TO Q9; TERMINATE AFTER Q12]**
6. Have you been prescribed Humalog 200 units/ml KwikPen at least once?
- Yes
 - No **[GO TO Q8; TERMINATE AFTER Q12]**
 - I don't know **[GO TO Q8; TERMINATE AFTER Q12]**
 - I don't have diabetes/I don't use insulin **[GO TO Q8; TERMINATE AFTER Q12]**
7. For how long have you been using Humalog 200 units/ml KwikPen?
- I have not used it yet
 - Less than 3 months
 - 3 – 6 months
 - 7 – 12 months
 - More than 1 year
 - I don't know

- I don't have diabetes/I don't use Humalog 200 units/ml KwikPen **[GO TO Q9; TERMINATE AFTER Q12]**
8. What type of insulin did you use prior to using Humalog 200 units/ml KwikPen?
- Humalog 100U/ml
 - Other 100U/ml insulin
 - I don't know/I don't remember
 - I don't have diabetes/I don't use Humalog 200 units/ml KwikPen **[TERMINATE AFTER Q12]**
9. What is your gender?
- Male
 - Female
10. What is the highest level of education you have completed?
- Some secondary school (or EU equivalent) or less
 - Finished secondary school
 - Some university or completed technical/trade school
 - Graduated university
 - Post graduate studies
 - Prefer not to answer
11. In what country do you live?
- [DROP-DOWN LIST INPUT WITH COUNTRIES TABLE]**
12. Which of the following groups best describes your age?

- Under 18 **[TERMINATE AFTER Q12]**
 - 18 – 29
 - 30 – 39
 - 40 – 49
 - 50 – 59
 - 60 – 69
 - 70 or older
 - Prefer not to answer **[TERMINATE AFTER Q12]**
13. Have you or any of your immediate family members ever worked for Eli Lilly and Company (Lilly), United BioSource Corporation (UBC), or the European Medicines Agency (EMA)?
- Yes **[TERMINATE]**
 - No
 - I don't know **[TERMINATE]**

[END SCREENING QUESTIONS]

[BEGIN SURVEY CONTENT]

[PREAMBLE 2]

The following questions are about Humalog 200 units/ml KwikPen.

14. Please answer True, False, or I don't know for each of the following statements about Humalog 200 units/ml KwikPen.

	[RANDOMISE LIST]	True	False	I don't know
A	Humalog 200 units/ml should only be injected using the			

prefilled KwikPen device in which it is supplied.

- B Your dose of insulin does not need to be converted when changing from one strength of Humalog to the other (for example, changing from Humalog 100 U/ml to Humalog 200 units/ml KwikPen).

15. Please answer Yes, No, or I don't know for each of the following statements about the patient communication titled *IMPORTANT SAFETY INFORMATION FOR Humalog 200 units/ml KwikPen (insulin lispro)*.

- | | Yes | No | I don't know |
|---|-----------------------|-----------------------|-----------------------|
| 
[RANDOMISE LIST]
 
[DISPLAY ONLY IN [ENTER COUNTRIES THAT DO NOT HAVE WEBSITE]]The first time I was prescribed Humalog 200 units/ml KwikPen, my doctor or nurse provided me with a paper copy of IMPORTANT SAFETY INFORMATION FOR Humalog 200 units/ml KwikPen (insulin lispro).
 |  |  |  |
| 
A [DISPLAY ONLY IN [ENTER COUNTRIES THAT HAVE WEBSITE]]The first time I was prescribed Humalog 200 units/ml KwikPen, my doctor or nurse provided me with a paper copy or told me to access the website to view IMPORTANT SAFETY INFORMATION FOR Humalog 200 units/ml KwikPen (insulin lispro).
 |  |  |  |
| 
B My doctor or nurse offered to explain the information in IMPORTANT SAFETY INFORMATION FOR Humalog 200 units/ml KwikPen (insulin lispro).
 |  |  |  |
| 
C I think about the important safety information for Humalog 200 units/ml KwikPen to remind myself of the risks when injecting my insulin.
 |  |  |  |

16. Other than the information you received from your doctor or nurse, from what sources have you received and/or accessed information on the safe use and understanding of the *Humalog 200 units/ml KwikPen*. Please select all that apply

Pharmacist

Other Medical Professional

Diabetes Support Group

Internet

Other

[PHONE ONLY: BEGIN SAFETY EVENT/PRODUCT COMPLAINT]

(INTERVIEWER: Please record if respondent spontaneously reported a safety event or product complaint during the course of this interview.)

- Yes
- No **[GO TO CLOSING 1a]**

Enter Safety Event or Product Complaint Verbatim

[MULTILINE INPUT]

(INTERVIEWER: Refer to Project Specific Procedure for next steps.)

[END SAFETY EVENT/PRODUCT COMPLAINT]

[CLOSING 1 DISPLAY ONLY IN [ENTER COUNTRIES OFFERING PAYMENT]]

We would like to send you [AMOUNT/TYPE] as compensation for your time and effort, but need your name and address to do so. Do you agree to provide your contact information for this purpose?

- Yes
- No **[GO TO CLOSING]**

FIRST NAME: **[FREE TEXT]**

LAST NAME: **[FREE TEXT]**

MIDDLE INITIAL: **[OPTIONAL; MUST BE 1-DIGIT ALPHA CHARACTER]**

ADDRESS: **[MULTILINE INPUT]**

CITY: **[FREE TEXT]**

COUNTRY: **[DROP-DOWN LIST INPUT WITH COUNTRIES TABLE]**

POSTAL CODE: **[FREE TEXT]**

[CLOSING 2]

This completes the survey. Thank you again for your participation.

[END SURVEY CONTENT]

**APPENDIX I.5 DIRECT HEALTHCARE PROFESSIONAL COMMUNICATION
ON THE CORRECT USE OF *HUMALOG 200 UNITS/ML KWIKPEN***

**APPENDIX I.6 PATIENT COMMUNICATION: IMPORTANT SAFETY
INFORMATION FOR HUMALOG[®] 200 UNITS/ML KWIKPEN[™] (INSULIN LISPRO)**

